3.4 Randomization

After informed consent, eligible patients will be randomized to receive a low or a standard dose of the assigned drug. Randomization will be centralized at the Istituto Mario Negri IRCCS, Milano. Randomization sequence will be created using SAS 9.4 (SAS Institute, Cary, NC, USA) statistical software and will be stratified by center with a 1:1 allocation using random block sizes of 4. Each center will receive randomization scratch-cards.

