treatment regimens. Numerical variables will be described using means, standard deviations, medians and ranges, while categorical variables using frequencies and percentages. The proportion of patients experiencing the primary end-point over the entire follow-up will be estimated using Kaplan-Meier survival curves. The difference between the two treatment arms in the proportion of patients experiencing the primary endpoint, with 95% confidence intervals (95% CI), will be calculated at 1, 3, 6, 9 and 12 months, and compared to the non-inferiority margin (m). In presence of variables at admission having a different distribution in the two treatment groups and that could have an effect on treatment response (possible confounders), a multivariable analysis will be also performed using a Cox's proportional hazards model, adjusted for these variables. A hazard ratio (HR), with the corresponding 95% CI, will be reported, and compared to a relative risk (RR) obtained considering as reference the proportion of patients experiencing the primary endpoint in the standard dose arm (p_0) and taking into account the non-inferiority margin ($RR=(p_0+m)/p_0$). The secondary end-point will be evaluated using Kaplan-Meier survival curves, comparing the two treatment arms with the log-rank test. In presence of possible confounders with a different distribution in the two treatment arms at baseline, a Cox's proportional hazards model will be used. The QOLIE-31 total score, the seven PSQ-18 subscales scores at the last visit, and mean daily patient's costs will be compared, separately, between treatment arms using the t-test, the Wilcoxon-Mann-Whitney test, or a multivariable linear regression model. Subgroup analyses will be performed separately for sex, age groups, drug, seizure types (focal/focal-to-bilateral), etiology (known/unknown), and center.

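### Section 10.4 lets chance baseline imbalance decide whether a second, Cox-based non-inferiority comparison is made and what it adjusts for, leaves center out, and gives that comparison the wrong hazard-ratio limit

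*Combined protocol and SAP*

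**What the plan says.** Section 10.4 sets out two comparisons for the primary endpoint.

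- **Always done.** The difference between arms in the proportion failing, from Kaplan-Meier curves, with 95% CI at 1, 3, 6, 9 and 12 months, is compared with m.
- **Done on a condition.** "In presence of variables at admission having a different distribution in the two treatment groups and that could have an effect on treatment response", the plan says that "a multivariable analysis will be also performed using a Cox's proportional hazards model, adjusted for these variables". The resulting hazard ratio and its interval "will be reported, and compared to a relative risk (RR) obtained considering as reference the proportion of patients experiencing the primary endpoint" in the standard-dose arm, that is with RR = (p0+m)/p0.

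For the adverse-event endpoint the arms are compared by log-rank test, and then: "In presence of possible confounders with a different distribution in the two treatment arms at baseline, a Cox's proportional hazards model will be used".

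The section gives no covariate list and no criterion for calling a distribution different. It does not say who judges a possible effect on response, or which result decides if the two primary comparisons disagree.

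Under Section 3.4 the allocation sequence "will be stratified by center with a 1:1 allocation using random block sizes of 4". The only use of center in Section 10.4 is in the subgroup list: "Subgroup analyses will be performed separately for sex, age groups, drug, seizure types (focal/focal-to-bilateral), etiology (known/unknown), and center".

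**The concern.** This is a stated selection rule, so the problem is not simply that a covariate list is missing. In a randomized trial, baseline differences between arms arise by chance. A rule that fits the model only when such differences are seen, and fills it only with the variables that differ, makes the second analysis depend on the data. Predictors that happen to be balanced are left out, although the case for adjusting for them does not depend on their balance.

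The Cox result is more than a description, because the plan compares it with its own non-inferiority limit. Readers of the report may therefore face one verdict or two, and the plan does not rank them. For the adverse-event endpoint the wording leaves open whether the Cox model is added to the log-rank test or replaces it; either way chance imbalance decides.

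Two further matters arise in the same text. The factor used to stratify randomization is not carried into any analysis model. And the limit for the hazard ratio is on the wrong scale.

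**Working it through.** **Inputs.** Section 10.6: 60% seizure-free in both arms (so failure p0 = 40%), one-sided 0.025, 80% power, 168 per arm, 10% dropout, 374 in total, and a margin of a relative 20% capped at an absolute 15%. Section 10.4: limit (p0+m)/p0. Section 3.4: center strata, blocks of 4.

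**1. The plan's own figure.** n per arm = (1.96 + 0.84)² × 2 × 0.60 × 0.40 / 0.15² = 168 (rounded up), with power 80.1%. Then 336 / 0.90 = 374. Both reproduce with m = 15 points, so the trial is sized on the unadjusted difference.

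**2. How often the trigger might fire.** The plan states no test. For illustration, assume a 5% threshold and k independent variables that are both collected and judged able to affect response. The chance that at least one differs is 1 − 0.95^k:

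- k = 6: 26%
- k = 10: 40%

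In simulations with 168 per arm and k = 10, it fired in about 40% of trials.

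**3. The hazard-ratio limit.** Under proportional hazards, failure of p0+m against p0 corresponds to HR = ln(1−p0−m)/ln(1−p0).

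| m | Plan's limit (p0+m)/p0 | Matching HR |
|---|---|---|
| 15 points | 0.55/0.40 = 1.375 | ln 0.45 / ln 0.60 = 1.56 |
| 12 points (20% of 60%) | 0.52/0.40 = 1.30 | ln 0.48 / ln 0.60 = 1.44 |

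A hazard ratio of 1.375 gives 12-month failure of 1 − 0.60^1.375 = 50.5%. The Cox comparison therefore works to a margin of about 10.5 points instead of 15.

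**4. Power of the Cox comparison.** Events: 336 × 0.40 ≈ 134. Power with equal arms ≈ Φ(√(134/4) × ln(limit) − 1.96).

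- Limit 1.375: about 45%
- Limit 1.56: about 74%
- m = 12, limit 1.30: about 33% (the risk difference has 61% at this margin)

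**5. Disagreement and its source.** With 40% failure in both arms, 10 covariates and imbalance called at p < 0.05, the triggered Cox verdict differed from the risk-difference verdict in about 36-37% of triggered trials, or 14-15% of all trials. An unadjusted hazard ratio against the same limit disagreed in 34-36%. Against the matching hazard ratio, disagreement fell to about 5-6% unadjusted and about 10% when triggered with prognostic covariates. Most of the conflict thus comes from the limit, and a smaller part from choosing covariates by imbalance.

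**6. Type I error.** With true failure of 55% against 40%, claiming non-inferiority on either verdict occurred in 2.7-2.8% of simulated trials, the same as for the risk difference alone.

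**7. Center.** With 1:1 blocks of 4, the arms within a center can differ by at most two patients. A rule that looks for imbalance would rarely select center.

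**The case against.** The strongest reply is that the primary result is safe. The risk difference is unconditional, the sample size rests on it, and the Cox model is described as an additional analysis. That stands. A reader might infer that the primary conclusion itself hangs on chance imbalance, or that a second route to success inflates the false-positive rate. The documents support neither: the first comparison is always made, and the second is stricter.

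A reader might also count every admission item in Section 3.5, take 15 to 20 of them at a 5% test, and conclude that the trigger fires in 54-64% of trials. That ignores the rule's second condition, a possible effect on response. Height or heart rate would not obviously qualify, and the text contains no 5% test. The 26-40% above is itself only an illustration.

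It is tempting to add that leaving out center and strong predictors makes the intervals too wide. This is not shown. In simulation, adjusting the Cox model for three true predictors raised the standard error of the log hazard ratio slightly, from 0.173 to 0.174-0.175. A standardized risk difference might gain precision. For center no gain can be computed, because the documents give neither the number of centers nor the variation between them. The planned 80% power already assumes no adjustment.

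Finally, center, seizure type and etiology are named in advance for subgroup analyses. That is to the plan's credit, but separate subgroup results do not adjust the main comparison or account for the stratification.

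**Conclusion.** The point holds within limits. The rule in Section 10.4 makes the existence and content of a second non-inferiority comparison, and the use of a Cox model for the adverse-event endpoint, a matter of chance, and it passes over the stratification factor. The harm is a verdict that may or may not appear and has no stated rank. The primary comparison is neither lost nor made less strict.

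The hazard-ratio limit is a separate error in the same text, and it is wrong as written: 1.375 where 1.56 would match, which leaves about 45% power beside 80%. These figures assume proportional hazards, p0 = 40%, no true difference between arms, and m = 15 points, the value that reproduces 168. At m = 12 the direction is the same. The trigger and disagreement rates rest further on an assumed threshold, number of covariates and independence.

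**What to change.** 1. Delete the imbalance trigger for both the primary and the adverse-event endpoint.
2. State that the 12-month risk difference against m is the decisive analysis.
3. Always fit one adjusted analysis, whatever the observed balance. Include center as a stratum, with small centers pooled by a rule set in advance, and a short list of baseline predictors fixed before outcomes are seen by arm. Seizure type and etiology, already named for subgroups, are natural candidates.
4. Report that analysis as a standardized 12-month risk difference with 95% CI against the same m. If a hazard ratio is kept, compare it with ln(1−p0−m)/ln(1−p0).
5. For the adverse-event endpoint, say in advance how the adjusted model stands beside the log-rank test.

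Sample size stays at 168 per arm and 374 in total, and the covariates are already part of the plan. This is a cheap improvement, though not free: Section 11.4 requires a written amendment with local ethics approval, the analysis takes slightly more work, and small centers may need pooling.

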2.3 Primary endpoint

The primary end-point is a treatment failure motivated by the need to change the assigned dose or the assigned drug for seizure relapse.

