10.6 Sample size calculation

The sample size is based on the primary efficacy end-point. The non-inferiority margin is a relative 20% difference, as stipulated by the ILAE, up to a maximum of an absolute 15% difference between the two dosing schedules for the primary endpoint. Assuming a one-sided p of 0.025 and that the proportion of patients who will not have a seizure in the low dose and standard dose groups is 60%, 168 patients per group provides 80% power to test whether a low AED dose is non-inferior

to a standard dose. Assuming 10% drop-out rate, the required sample size will be 374 patients.

11 Administrative procedures

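### Section 10.4 judges the adjusted hazard ratio against a limit on the cumulative-risk scale, so at the planned 40% failure rate the supplementary Cox analysis allows only about 70–73% of the margin m

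*Combined protocol and SAP*

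**What the plan says.** The primary endpoint is defined in section 2.3: "The primary end-point is a treatment failure motivated by the need to change the assigned dose" or drug because of seizure relapse. Section 10.4 gives two routes to a non-inferiority statement.

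- **Kaplan-Meier route.** "The proportion of patients experiencing the primary end-point over the entire follow-up will be estimated using Kaplan-Meier survival curves". For the between-arm difference, with its 95% CI, the rule is: "will be calculated at 1, 3, 6, 9 and 12 months, and compared to the non-inferiority margin (m").
- **Cox route, conditional.** "In presence of variables at admission having a different distribution in the two treatment groups", and where those variables could affect treatment response, "a multivariable analysis will be also performed using a" Cox model adjusted for them. Its hazard ratio, with 95% CI, is handled as follows: "and compared to a relative risk (RR) obtained considering as reference the proportion of patients experiencing the primary endpoint in the standard dose arm". Writing p0 for that reference value, the formula is RR=(p0+m)/p0.

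Section 10.6 supplies m: "The non-inferiority margin is a relative 20% difference, as stipulated by the ILAE, up to a maximum of an absolute 15% difference". It plans on the basis that "the proportion of patients who will not have a seizure in the low dose and standard dose groups is 60" per cent.

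Section 10.4 gives no conversion between the risk scale and the hazard scale. It does not say whether p0 is the planned or the observed value, or which result stands if the two routes disagree.

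**The concern.** The ratio (p0+m)/p0 is the largest acceptable ratio of cumulative failure risks. A hazard ratio is close to a risk ratio only when events are rare, and this trial plans for about 40% failures. Under proportional hazards, a hazard ratio above 1 always exceeds the risk ratio that it produces. A hazard ratio held to the risk-ratio limit is therefore held to a smaller difference than m.

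What is at stake is a contradictory report. A low dose that is truly non-inferior could meet m on the Kaplan-Meier difference and miss the limit in the adjusted model, mainly because that limit is on the wrong scale. Choosing between the two results after the data are seen would look post hoc.

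**Working it through.** **Inputs.** From section 10.6: one-sided 0.025, 80% power, 60% seizure-free in both arms, 168 per arm, 10% drop-out, 374 in total. From section 3.5: 12 months of follow-up. The margin can be read three ways in section 10.6: 15 points (the cap), 12 (20% of 60) or 8 (20% of 40).

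**Assumptions.** p0=1−0.60=0.40, which counts every relapse as a primary-endpoint failure; proportional hazards; limit evaluated at 12 months.

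**1. The plan's own figure.** n per arm = (1.960+0.8416)² × 2 × 0.60 × 0.40 / m² = 7.849 × 0.48 / m².
- m=0.15: 167.4, so 168; 336/0.90 = 373.3, so 374. Both stated figures reproduce.
- m=0.12: 262 per arm. m=0.08: 589 per arm.

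Only 15 points gives the stated size, but the scale problem is shown for all three readings.

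**2. What the limit allows.** Under proportional hazards the low-dose failure risk is 1−(1−p0)^HR. The difference allowed by the plan's limit is therefore 1−0.60^RR−0.40. The hazard ratio that matches m is ln(1−p0−m)/ln(1−p0).

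| m (points) | Plan's limit (0.40+m)/0.40 | Hazard ratio matching m | Difference allowed by plan's limit | Share of m |
|---|---|---|---|---|
| 15 | 1.375 | ln 0.45/ln 0.60 = 1.563 | 10.5 points | 70% |
| 12 | 1.300 | ln 0.48/ln 0.60 = 1.437 | 8.5 points | 71% |
| 8 | 1.200 | ln 0.52/ln 0.60 = 1.280 | 5.8 points | 73% |

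**3. Dependence on p0 (m=15).** The share of m is 82% at p0=0.20, 76% at 0.30, 70% at 0.40 and 63% at 0.50.

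**4. Chance of meeting the limit with equal arms.** Events: 0.40 × 336 ≈ 134, so SE(log HR) ≈ 2/√134 = 0.173. Power = Φ(ln(limit)/SE − 1.96).
- m=15: 45% against 1.375, 73% against 1.563; 80% for the difference in proportions.
- m=12: 33%, 55% and 61%.
- m=8: 18%, 30% and 32%.

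**5. How often the two routes disagree.** Simulations used 168 per arm, equal arms, 40% failure, exponential times, no drop-out and observed p0. The entries are trials in which the 12-month Kaplan-Meier difference meets m but the hazard ratio misses the plan's limit, for m=15/12/8.
- Unadjusted Cox model in every trial (10,000 trials): about 35%, 30%, 14.5%.
- Adjusted model, only in trials with imbalance (20,000 trials; five assumed binary factors, hazard ratio 1.5 each, trigger p<0.05): 35%, 30%, 16%. The reverse disagreement was at most 0.6%.

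Some disagreement has other causes. With the matching hazard-ratio limit, total disagreement in either direction is 6%, 7%, 5% (unadjusted) or 10%, 13%, 12% (adjusted, triggered). With a standardised 12-month risk difference it is 3%, 5%, 4% or 8%, 11%, 11%.

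**6. How often the model would be run.** The documents do not allow an estimate. With 1, 5 or 10 assumed factors the trigger fires in 6%, 26% or 44% of trials. For m=15, multiplying by about 0.35 gives conflict in about 2%, 9% or 15% of all trials.

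**7. Direction of the error.** With the low dose truly m worse under proportional hazards (unadjusted model), the plan's limit is wrongly met in 0.1%, 0.2% or 0.5% of trials. The matching limit gives 1.9% for each m, and the Kaplan-Meier difference gives 2.6%, 2.6% and 2.3%.

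**The case against.** The strongest reply is that little depends on this analysis. The Cox model is additional and conditional, the Kaplan-Meier difference is compared with m whatever the model shows, and section 10.4 does not call the hazard ratio a second test of non-inferiority. All of that stands, and it limits the severity.

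The size is also conditional. Section 10.6 plans on freedom from seizures, while section 2.3 counts a change of dose or drug for relapse. Sections 6.6 and 7.2 leave modification after a relapse to the treating physician. If some relapses lead to no change, p0 is below 0.40 and the mismatch shrinks. This stands too, but even at p0=0.20 and m=15 the limit allows only 82% of m.

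Switching to the matching hazard-ratio limit is not a clean cure. An adjusted hazard ratio is conditional on the covariates: with five factors of hazard ratio 1.5, all adjusted for, the value that gives 15 points is 1.61, not 1.563. If the arms diverge only after month 6 or 9 (an assumed shape; unadjusted, m=15, low dose truly 15 points worse at month 12), the matching limit is wrongly met in about 4% or 6% of trials. The plan's limit is wrongly met in 0.4% or 0.6%.

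A reader might infer more than the documents support:
- **That the trial could falsely claim non-inferiority.** The limit is stricter than m under proportional hazards, and it stayed strict in the late-divergence cases above.
- **That the primary analysis or sample size is wrong.** Neither uses the RR limit, and 168/374 reproduces.
- **That a third of trials would give conflicting results.** The 35% applies only if the model is run, the arms are equal and m=15.
- **That meeting m at any one of five times would suffice.** Section 3.5 sets 12 months of follow-up and section 10.4 defines the outcome over that follow-up, so month 12 is the natural deciding time, although 10.4 does not say so.

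**Conclusion.** The hazard-ratio comparison is on the wrong scale as written. At p0=0.40 and 12 months, under proportional hazards and with every relapse counted as a failure, the supplementary analysis applies 70–73% of m. The algebra is certain given those conditions. The practical frequency is not, because it depends on an imbalance trigger that section 10.4 does not define and on prognostic factors that had to be assumed.

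The consequence is a possible discordant supportive result, not a threat to the validity of the main comparison. Severity is minor to should-fix: the effect is confined, but the rule is stated explicitly and is cheap to correct. Which of 15, 12 or 8 points is meant is a separate question that this point does not settle.

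**What to change.** In section 10.4, replace the comparison of the hazard ratio with RR by text such as:

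*The covariate-standardised 12-month risk difference from the adjusted model (for example a Cox model stratified by arm, which avoids assuming proportional hazards for treatment), with 95% CI by bootstrap or delta method, will be compared with m. This analysis is supportive; non-inferiority is decided by the 12-month Kaplan-Meier difference compared with m. Differences at 1, 3, 6 and 9 months are descriptive.*

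The adjusted hazard ratio with its CI can still be reported. If a hazard-ratio limit is kept, use ln(1−p0−m)/ln(1−p0), define p0 as the 12-month proportion in the standard dose arm, and say whether it is planned or observed. State also that this limit assumes proportional hazards, is only approximate for an adjusted hazard ratio, and can be anti-conservative if the arms diverge late.

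The cost is a few sentences and some programming for the standardised interval, with no effect on patients, data collection or sample size. A formal comparison with m before month 12 is given up. Some disagreement between routes will remain: the figures in step 5 are for a standardised difference from a proportional-hazards model, and the arm-stratified version was not simulated. The change should be made before unblinded results are seen.

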2.2 Secondary objectives

To demonstrate that the proportion of patients experiencing intolerable drug-related adverse events is lower with a low than a standard dose.

To demonstrate that health-related quality of life (HRQOL) and satisfaction with treatment score higher with a low than a standard dose.

To demonstrate that, on a societal perspective, the treatment of newly diagnosed epilepsy with low AED doses will translate into savings in terms of contacts with the National Health System (in- and outpatient visits, drug expenditures).

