2.4 Secondary endpoints

Secondary endpoints include: 1. Treatment failure motivated by intolerable drug-related adverse events; 2. HRQOL total score at 12 months; 3. Patient's satisfaction at 12 months; 4. Total cost of health care resources consumed for the management of epilepsy during the first 12 months of the study.

3. Study design

This is a multicenter randomized pragmatic parallel-group single-blind non-inferiority trial. Italian epilepsy centers will participate in the study. Each center has been selected on the basis of high

standards in the management of epilepsy and on previous participation to studies coordinated by the PI.

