3.6 Baseline and follow-up visits

At the baseline visit (Visit 1), each patient with newly diagnosed epilepsy will be screened for eligibility. Patients satisfying all the selection criteria will be informed of the study aims and asked to release a written informed consent. All the baseline data will be collected in an electronic case report form (e-CRF) and the patient will be then randomized. Follow-up visits will be scheduled at the discretion of the caring physician but telephone contacts will be programmed at 4 weeks, 3, 6, 9 and a clinic on-site visit at 12 months. An interval of \pm 1 week for the visit schedule is permitted. During each contact/visit the patient will be asked to report any seizure recurrence, adverse event and any additional information deemed important for the management of the disease. Patients will be invited to read the diaries and verify if any missing or incomplete information was present.

4. Study duration

Study duration: 36 months as indicated below:

- Administrative and ethical procedures: 6 months.
- Duration of patient enrolment: 12 months.
- Follow-up period: 12 months from the date of randomization.
- Database lock and statistical analysis: 30th-35th month.
- Final report and data publication: 36th month.
- Planned start of enrolment: as soon as the Ethics committee approval and signed contract are in house.

The end of study is considered the last patient last visit (LPLV).

5. Study population

Total number of patients: 374 considering 10% of expected dropouts.

Number of patients for each treatment arm = 168 (see Sample Size calculation for details).

6. Drug choice, tapering and maintenance daily dosages

The choice of the drug is left to the caring physician's discretion but it must be limited to the AEDs marketed for monotherapy use. All the study drugs will be used according to the respective SPCs, which will be sent by the promoter to all the study investigators.

For each individual drug, the following doses (in mg/day) have been selected as low vs. standard: carbamazepine, 300 vs 600; levetiracetam, 500 vs. 1000; valproate, 300 vs. 600; zonisamide, 150-300; oxcarbazepine, 600 vs. 1200; topiramate, 100 vs. 200; lamotrigine, 100 vs. 200; gabapentin, 450 vs. 900, lacosamide 100 vs. 200. Tapering to the assigned target dose will be performed as in

clinical practice but instructions will be imparted for each drug at the beginning of the study.

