10.4 Outcome measures, statistical methods and data analysis

Expected outcomes are the following:

1. compared to patients assigned to standard daily doses, patients receiving low daily doses of AEDs are expected to incur in similar rates of seizure recurrence;
2. compared to patients assigned to standard daily doses, patients receiving low daily doses of AEDs are expected to undergo significantly less treatment changes due to intolerable drug-related adverse events;
3. compared to patients assigned to standard daily doses, patients receiving low daily doses of AEDs are expected to experience less drug-related intolerable adverse events;
4. compared to patients assigned to standard daily doses, patients receiving low daily doses of AEDs are expected to experience a better quality of life;
5. the National Health System is expected to incur in significant savings with low daily doses of AEDs.

Primary outcome

The proportion of patients experiencing a treatment failure motivated by the need to change the assigned dose or the assigned drug for seizure relapse during the follow-up.

Secondary outcomes

1. the proportion of patients experiencing a treatment failure motivated by intolerable drug-related adverse events during the follow-up;
2. QOLIE-31 total score at the last visit;
3. the score of the seven PSQ-18 subscales (general satisfaction, technical quality, interpersonal manner, communication, financial aspects, time spent with doctor, accessibility and convenience) at the last visit;
4. the mean daily patient's cost of health care resources consumed for the management of epilepsy during the first 12 months of the study.

Descriptive statistics will be provided for all the data collected at admission, comparing the two

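### Section 10.4 lets the cost comparison rest on a Wilcoxon-Mann-Whitney test, which does not assess the difference in mean cost that a savings claim needs

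*Combined protocol and SAP*

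**What the plan says.** The cost question is set out in four places:

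- Section 2.2 aims to show that low doses "will translate into savings in terms of contacts with the National Health System (in- and outpatient visits, drug expenditures").
- Section 2.4 names the endpoint: "Total cost of health care resources consumed for the management of epilepsy during the first 12 months of the study".
- Section 10.4 lists the expected result, that "the National Health System is expected to incur in significant savings with low daily doses of AEDs".
- Section 10.4 then defines the outcome as "the mean daily patient's cost of health care resources consumed for the management of epilepsy during the first 12 months of the study".

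On the method, Section 10.4 says that "mean daily patient's costs will be compared, separately, between treatment arms using the t-test, the Wilcoxon-Mann-Whitney test, or a multivariable linear regression model". The same sentence covers the QOLIE-31 and PSQ-18 scores. It gives no rule for choosing among the three methods, and no difference in mean cost with a confidence interval is promised.

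The doses are in Section 6. The first six drugs are given as "carbamazepine, 300 vs 600; levetiracetam, 500 vs. 1000; valproate, 300 vs. 600; zonisamide, 150-300; oxcarbazepine, 600 vs. 1200; topiramate, 100 vs. 200". For the remaining three drugs the same list has "lamotrigine, 100 vs. 200; gabapentin, 450 vs. 900, lacosamide 100 vs. 200". The protocol gives no unit costs and no costing method.

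**The concern.** A payer's saving is the difference in mean cost per patient multiplied by the number of patients, so the relevant null hypothesis is equal arithmetic means. The t-test and linear regression on untransformed cost address that null. The Wilcoxon-Mann-Whitney test does not. It asks whether a randomly chosen low-dose patient tends to rank below a randomly chosen standard-dose patient, and an admission counts as one high rank whatever the bill.

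The two questions can have different answers in this trial. Allocation halves the amount of drug, so drug spending may fall a little for nearly everyone on low dose. Any extra cost of relapse care would fall on a minority and be large. A small shift in most patients set against rare large costs is where ranks and means part company. At stake is a stated objective with consequences for a payer: a significant saving could be reported when the health service spends the same or more.

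**Working it through.** **1. The plan's own figure.** Section 10.6 ("Assuming a one-sided p of 0.025", 60% seizure-free in both arms, 80% power, 15-point cap on the margin):

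n = 2 × 0.60 × 0.40 × (1.960 + 0.842)² / 0.15² = 0.48 × 7.849 / 0.0225 = 167.4, so 168 per arm; 336 / 0.90 = 373.3, so 374.

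This reproduces. It concerns the primary endpoint only; no figure is given for cost. I use 168 per arm below.

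**2. Dose ratios.** 300/600, 500/1000, 300/600, 150/300, 600/1200, 100/200, 100/200, 450/900 and 100/200 all equal 0.5. Zonisamide is written as a range; I read it as low versus standard.

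**3. A worked example (all costs assumed).** Annual drug cost averages 200 on standard dose and 100 on low dose (log-SD 0.5 between patients). There are two visits at 20 each, and an admission costs 3000 on average.

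- Standard, 10% admitted: 200 + 40 + 0.10 × 3000 = 540.
- Low, equal mean: 100 + 40 + p × 3000 = 540, so p = 13.3%.
- Low, dearer by 150: 100 + 40 + p × 3000 = 690, so p = 18.3%.

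In simulated trials with equal means, Wilcoxon is significant in favour of low dose in 100% and the t-test in 2.9%. With low dose dearer by 150, the figures are 100% and 0.2%.

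**4. How far this depends on the assumptions.** In a second model, cost = drug + routine care + occasional acute episode. Standard drug cost is 1 unit and low-dose drug cost is r. Routine care averages 0.5 to 4 units. An episode costs A = 4, 6 or 10 units and occurs in 10% on standard dose. Means are equal when the low-dose episode rate is 0.10 + (1 − r)/A; for r = 0.5 and A = 4, that is 0.10 + 0.125 = 22.5%. Tests are two-sided at 5%, so the nominal rate in favour of low dose is 2.5%.

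| Assumption, true means equal | Wilcoxon favours low dose |
|---|---|
| Drug CV 0.4, routine CV 0.5, routine 0.5-2, r = 0.5 | 32-100% |
| As above, r = 0.7 | 17-99% |
| As above, routine 4, r = 0.5-0.7 | 4-20% |
| Drug CV 1.0, routine CV 1.0, routine 0.5-4 | about 3-74% |
| Drug CV 1.5, routine CV 1.0, routine 0.5-4 | about 2-30% |
| Drug costs equal (model of step 3) | 3.0% |

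Welch favours low dose in about 2-4% in the second model.

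Now let low dose be truly dearer: r = 0.5, A = 6, episodes 22.5% v 10%, so 0.125 × 6 − 0.5 = +0.25 unit. Wilcoxon still favours low dose in 99.9%, 89% and 26% of trials (routine 0.5, 1, 2) with the narrow spreads, but in only about 23%, 11% and 2% with both CVs at 1.0.

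**5. Could non-inferiority be declared in the same trial?** Take 40% failure on standard dose and a true excess d on low dose, and assume that each extra costly episode is an extra primary failure.

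P = Φ((0.15 − d)/SE − 1.96), with SE = √[(0.40 × 0.60 + (0.40 + d)(0.60 − d))/168].

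- d = 0.03: SE = 0.0537; 0.12/0.0537 − 1.96 = 0.27; P = 61%.
- d = 0.05: SE = 0.0539; 0.10/0.0539 − 1.96 = −0.10; P = 46%.
- d = 0.08: SE = 0.0540; 0.07/0.0540 − 1.96 = −0.66; P = 25%.
- d = 0.125: SE = 0.0540; 0.025/0.0540 − 1.96 = −1.50; P = 7%.

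If the 20% relative margin applies instead (0.20 × 60% = 12 points), the last figure is about 2%.

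**The case against.** **The test is only permitted.** One generic sentence covers three kinds of outcome, nothing assigns the rank test to cost, the outcome is worded as a mean, and two of the three methods target the mean. This stands, and it confines the defect to one option. That analysts would pick the rank test for skewed costs is a matter of habit, not something the protocol says. But naming a main method cures the problem only if a mean-based one is named.

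**The high rates need homogeneous costs.** This also stands. Physicians choose among nine drugs, brand or generic (Section 6.5), with regional reimbursement (Section 6.7), so drug costs may vary widely. Half the dose need not mean half the price. The table shows how quickly the effect fades.

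**The relapse excess may not occur.** Section 10.4 expects similar relapse rates, and Section 10.5 provides for stopping if low dose has more relapses. Section 1 reports more treatment changes on standard doses in the earlier trial, mostly from adverse events; that would add cost to the standard arm and is not in the model. Patients also leave the study at relapse (Section 7.2), whereas the simulation uses complete annual costs. The calculation therefore shows what the test can do, not what is likely.

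**Stronger readings.** A reader might infer that any excess within the margin would let the trial claim non-inferiority and savings together. The documents do not support that: the margin limits the confidence bound, not the true excess, and step 5 shows non-inferiority becoming rare at large excesses. A reader might also take 17-100% as the expected error rate; the protocol fixes none of the inputs behind it.

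**Conclusion.** The concern holds in this form: a listed test for cost does not assess mean or total cost, and the halved doses give a concrete route by which it could show a saving that is absent. It needs two conditions: lower drug cost for most low-dose patients, and some excess of rare, costly care on low dose.

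The size cannot be fixed from the documents. With equal true means, the rate at which Wilcoxon favours low dose runs from about nominal (equal drug costs, dominant routine care or very variable drug costs) to nearly 100% (homogeneous drug costs, little routine care). A joint finding of non-inferior and cheaper is plausible only at modest true relapse excesses, such as 3 to 5 points with the 15-point margin. This affects a secondary endpoint, not the primary analysis, and should be corrected before the data are analysed.

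**What to change.** Add to Section 10.4, for the cost outcome only: any statement about savings will rest on the difference between arms in arithmetic mean cost per patient, with a 95% CI from a bootstrap of patients within arm, a Welch t-test, or linear regression on untransformed cost, one of these to be named in advance. Savings will be claimed only if the interval excludes zero in favour of low dose. Rank tests and medians for cost are descriptive. Drug and non-drug cost are reported separately beside the total, so that the part that follows directly from allocation is visible.

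The listed linear regression can stay, since it already targets the mean. The change takes a few sentences and a few lines of code, with no new data or visits. The downside is a wider interval for skewed costs, so savings become harder to claim.
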